#### **The deep suturing approach (32 patients)**

A vertical elliptical incision encompassing all pilonidal pits will be made and excision of the sinus will be carried out down to the level of the sacrococcygeal fascia. Tension will be released by a limited sharp dissection above the fascia. After haemostasis is ensured using electrocautery, a suction drain will be inserted through a separate incision, then the deep fascia will be approximated and the wound will be closed in layers using polyglactin 0 sutures. Finally, the skin will be closed with 2/0 polypropylene interrupted mattress sutures.

#### **Postoperative care and follow-up**

Standard postoperative care, including mobilization and return to normal diet as quickly as possible will be recommended. Early postoperative complications (bleeding and urine retention) will be noticed and recorded. Pain score and early wound infection will be recorded. Post-operative pain will be assessed on the first, fourth postoperative day and at stitch removal using a visual analogue scale (VAS) from zero (no pain) to 10 (worst pain imaginable) (10).

Patient will be discharged usually on the next day. Oral antibiotics and analgesics will be prescribed on patient's discharge. All the patients will be advised to shave the area around the operative site at least monthly.

All the patients will be recommended to visit the outpatient clinic twice weekly for two weeks then weekly for another two weeks and then every 1 month during the follow-up period (6 months). During each visit, complete patient assessment will be done. If any complications are detected (seroma, recurrence, wound dehiscence), it will be recorded as well.

Infection will be considered as leakage of purulent secretion through the surgical wound and not only peri-incisional hyperaemia. The suction drain will be removed when drainage became less than 20 mL per day (11). Seroma will be defined as the formation of non-infected serous fluid collection beneath the flap and diagnosed by clinical examination (12).

Duration of incapacity for work will be defined as the date on which patient returned to normal activities including employment and leisure activities time from the date of surgery. In addition, patients will be asked to evaluate the cosmetic appearance of the wound by looking at its picture using VAS ranging from 0-10 where 0 means the worst cosmetic outcome and 10 indicates the best cosmetic outcome. A Turkish study used a 0 to 10 visual analogue scale (VAS) scale to assess patient satisfaction with their cosmetic outcome (13).

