**The rhomboid flap Approach (32 patients)**

The patient will be operated on under spinal anesthesia. The patients will be placed in prone jack-knife position on the operating table with the legs slightly abducted and the buttocks strapped apart by adhesive tapes. The anus will be excluded from the operative field by surgical drapes. The pathologic area to be excised will be marked. This area will be

enclosed by a rhombus shape with the long axis in the midline (ABCD). Lines  $AB = BC = CD = DA$  will be equal to each other, with the axis AC being along the natal cleft. Line BD will be extended transversely and then the line EF will be drawn equal in length. The rhombus containing the pilonidal sinus will be then excised down to the periosteum in the midline and gluteal fascia laterally. Meticulous hemostasis will be done by means of electrocautery.

The flap will be dissected deep to the gluteal fascia (subfascial level) so as to raise thick a fasciocutaneous flap. This will assure good vascularity of the flap without dead space. The rhomboid flap (CDEF) will be mobilized from the gluteal fascia and sutured without tension in three layers (gluteal fascia with 2/0 Vicryl, subcutaneous fat with 3/0 Vicryl, and the skin with 4/0 Prolene). As all sides will be equal in length, the flap fits in place without tension. A suction drain will be left behind and the wound will be dressed as usual. Pressure wound dressing will be applied and removed on the third postoperative day.

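### The only seroma definition requires a flap, so the deep-suturing arm has no written seroma criterion

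*Protocol*

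**What the plan says.** Under Postoperative care and follow-up (section 2.4.4) the protocol gives its only seroma criterion: "Seroma will be defined as the formation of non-infected serous fluid collection beneath the flap and diagnosed by clinical examination".

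The same section applies one follow-up to both arms: "All the patients will be recommended to visit the outpatient clinic", then "During each visit, complete patient assessment will be done", and "If any complications are detected (seroma, recurrence, wound dehiscence), it will be recorded as well". None of this is restricted by arm. Section 2.4.5 b lists the incidence of other complications as the third secondary outcome, and section 2.2 states the aim as a comparison of the two techniques.

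The two operations differ on the point that matters here:

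- Rhomboid arm: a flap is raised. "The flap will be dissected deep to the gluteal fascia (subfascial level").
- Deep-suturing arm: an elliptical excision, then "Tension will be released by a limited sharp dissection above the fascia", then "a suction drain will be inserted through a separate incision" and layered closure. No flap is mentioned.

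**The concern.** A complication compared between randomised arms needs one criterion that can be met in both. Here the location part of the definition can be met only in the rhomboid arm. Two readings are open to an assessor, and neither is satisfactory:

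- **Literal.** A collection under a deep-sutured wound does not meet the definition. Seroma in that arm is under-counted and the comparison tilts against the flap.
- **Loose.** The assessor drops or replaces the location phrase. The deep-suturing arm is then scored on an unwritten rule that may differ between assessors, and the direction of any error is not fixed.

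Diagnosis is by clinical examination, already a matter of judgement, and the protocol describes no blinding of assessors. That leaves the written definition as the main safeguard.

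**Working it through.** **Step 1: the wording.** This settles the point without arithmetic.

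| Element of the definition | Rhomboid arm | Deep-suturing arm |
|---|---|---|
| Not infected | can be met | can be met |
| Serous collection | can be met | can be met |
| Found on clinical examination | can be met | can be met |
| Located under the flap | can be met | cannot be met: no flap |

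No other seroma criterion appears in the protocol. The limited dissection in the deep-suturing arm is not called a flap, so it does not fill the gap. A drain is placed in that arm, so fluid there is foreseen. The neighbouring infection definition avoids the problem, because it refers to the wound and not the flap: "Infection will be considered as leakage of purulent secretion through the surgical wound".

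**Step 2: an illustration of size.** The protocol states no seroma rate, so there is no figure to reproduce.

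*Inputs from the protocol:* 32 patients per arm (sections 2.4.3 c and 2.4.4); significance at p < 0.05 and the χ² and Fisher tests (section 2.5).

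*Assumed inputs:* a true seroma rate p equal in both arms (5%, 10%, 15%, 20%), and a share s of deep-suturing collections that go uncounted (0, 0.25, 0.5, 1).

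*Method:* X ~ Bin(32, p) for the flap arm and Y ~ Bin(32, p(1 − s)) for deep suturing. Sum P(X = x)·P(Y = y) over all pairs with x > y and two-sided p-value < 0.05.

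Chance of a false significant flap excess, Fisher's exact test:

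| Share uncounted | p = 5% | 10% | 15% | 20% |
|---|---|---|---|---|
| 0 (neutral definition) | 0.1% | 0.5% | 1.0% | 1.2% |
| 0.25 | 0.1% | 1.1% | 2.5% | 3.8% |
| 0.5 | 0.2% | 2.3% | 6.2% | 10.9% |
| 1 (upper bound) | 0.5% | 9% | 35% | 64% |

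The mean number of uncounted seromas is 32·p·s. At s = 0.5 this is 0.8, 1.6, 2.4 and 3.2 across the four rates.

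**Step 3: which χ² test.** Section 2.5 does not say whether χ² is continuity-corrected. The corrected version differs from Fisher by less than 0.1 percentage point in every cell above. The uncorrected version gives larger figures:

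| Share uncounted | p = 5% | 10% | 15% | 20% |
|---|---|---|---|---|
| 0 | 1.6% | 2.8% | 2.7% | 2.5% |
| 0.25 | 2.3% | 5.7% | 6.8% | 7.6% |
| 0.5 | 3.5% | 11% | 16% | 20% |
| 1 | 7% | 40% | 73% | 91% |

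The events needed in the flap arm against 0/32 show why:

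- Fisher: p = 2·C(32,k)/C(64,k), which is 0.053 at k = 5 and 0.024 at k = 6, so six events are needed.
- Corrected χ²: p = 0.062 at k = 5 and 0.032 at k = 6, so six again.
- Uncorrected χ²: at k = 4 the statistic is 64·4²·32²/(32·32·4·60) = 4.27, p = 0.039, so four are enough.

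The Fisher figures are therefore the cautious ones.

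**Step 4: the other direction.** If a loose rule over-counted deep-suturing seroma by a quarter (rate 1.25p), Fisher would show a false significant deep-suturing excess in 0.3%, 1.5%, 2.8% and 4.0% of trials at the four rates. This shows only that the sign is not fixed. Nothing in the protocol makes over-counting likely.

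**The case against.** The strongest reply is that this hardly matters in practice. Three of the four elements carry over to either wound, every patient is fully assessed, and any complication found is recorded. A sensible clinician would note a serous collection under a midline closure as a seroma. That is fair, and it is why literal scoring is treated here as the less likely practice. It does not supply the missing criterion: what would be applied in that arm is still unwritten.

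A second reply is that the numbers rest on invented rates and shares, and that the top figure needs every deep-suturing seroma to be missed. This also stands. The tables are illustration only, and the defect does not depend on them. The over-count scenario is the weakest part, since no mechanism for it is apparent.

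Third, the protocol does not call for a separate test of seroma. It names other complications as a group. If these were pooled per patient, the effect would be diluted. That is a further reason to keep the rating low.

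Nor can the point be left to a statistical analysis plan: the protocol has already fixed a definition, in terms that fit one arm only.

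**Conclusion.** The point holds, as a minor defect in an outcome definition. That the wording fails to cover the deep-suturing arm is certain from the text. The size of any bias is not known, because the protocol gives neither a seroma rate nor a basis for the share miscounted. Under the assumed rates the effect is negligible when seroma is rare or few cases are missed. It becomes material only if rates are around 15% to 20% and half or more of the deep-suturing collections go uncounted, or at lower values if the χ² test is used uncorrected. The damage is confined to the seroma component of the third secondary outcome. Recurrence, the sample size and the infection definition are untouched.

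**What to change.** Use one seroma definition for both arms. Keep the three elements that already apply to everyone and extend the location phrase to read *under the flap or under the sutured wound*. Put the same wording in the protocol and the case report form before outcomes are assessed. The cost is one phrase in each document, with no added visit, test or procedure.

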#### 2.4.5 –Research outcome measures:

##### a. Primary (main):

Postoperative recurrence rate. Recurrence will be defined as the additional outbreak of signs and symptoms of pilonidal disease after a disease-free interval following complete wound healing (8).

##### b. Secondary (subsidiary):

1. Operative time.
2. Postoperative pain.
3. The incidence of other complications.
4. Postoperative cosmetic outcome.
5. The duration to walk, sit on toilet free from pain.
6. The duration till complete daily activities.

#### 2.5-Data management and analysis (Details needed):

##### Data collection

Data will be collected by the principal investigator from Assiut University Hospital from.

##### Computer software

We will use SPSS version 26 for analyzing the data.

##### Statistical tests

Quantitative data will be presented as means  $\pm$  SD. Categorical and binary variables will be tested using the  $\chi^2$  test and Fisher's exact test. Statistical significance will be assumed when  $p < 0.05$ .

**Part 4: Funding (Mandatory for those requesting funding from Grant Office)**

**4.1. Total funds requested:** LE

**4.2. Author responsible for managing the budget/grant (Cannot be a resident):**

Name			
Department			
e-mail		Mobile	

**4.3. Budget Details**

**Cost**

- Research equipment and accessories
- Chemicals/Medications
- Data entry
- Statistical analysis

**4.4. All researchers' International publications in the last 3 years.**

	Title	Journal	Impact Factor
1			
2			
3			
4			
5			

**(Add others if required)**

**4.5. Details of Previously Obtained Grants (institutional or others):**

	Title	Name of Applicant for grant	Date obtained	Finished Yes/No	Published Yes/No
1					
2					
3					
4					

**(Add others if required)**

**4.6. Research reporting timetable (Mandatory if applying for a fund):**

Activity (Other activities may be added)	Time required (Months)											
	2	4	6	8	10	12	14	16	18	20	22	24
Preparation and development of Material												
Training of personnel involved in the research (if needed)												
Research work (Clinical, lab work or field work)												
Data entry and analysis												
Research writing												
Publication												

\* Numbers indicates the time in months needed to complete each part of the project.

\* Please half squares corresponding to time required for each specific action

يتعهد الباحثون بنشر نتائج البحث الممول من وحدة تمويل الأبحاث في إحدى الدوريات العلمية المحكمة والمدرجة على قاعدة Scopus أو Web Of Science في خلال الفترة الزمنية المحددة في البند السابق من قبلهم والايتم خصم مبلغ التمويل من مرتباتهم بالتساوى فيما بينهم كما يتعهدوا بالإشارة الى مساهمة وحدة تمويل الأبحاث بكلية طب أسيوط عند نشر البحث.

Faculty of Medicine  
Institutional Review Board (IRB)

**\*\*Choose at least 1 from each of the 3 groups below**

Group 1	Group 2	Group 3
1.1- Conception and design 1.2- Acquisition of data 1.3- Analysis and interpretation of data	2.1- Drafting of the submitted protocol 2.2-Critical revision of the submitted protocol for important intellectual content	3.1- Statistical analysis 3.2- Obtaining funding 3.3- Administrative, technical, or material support 3.4- Supervision 3.5- Other (specify)

**After completing the application form, please**

1. Record the completed and revised application form on a CD and present to the Vice Dean Research Office.

## Faculty of Medicine Institutional Review Board (IRB)

2. **All authors should sign a printed copy** of the completed application form that should be presented as well to the Vice Dean Research Office.
3. A **copy** of the printed and signed research application form should be presented to the **Ethical Committee**.
4. It is the applicant responsibility to make sure that the application form is fully and accurately completed and that all other supporting documents or formalities are completed in due time.
